6.7.2 Toxicities Requiring ASP1948 Treatment Interruption

ASP1948 treatment will be withheld for the following toxicities if there is a reasonable possibility that the event may have been caused by ASP1948:

- Grade 4 neutropenia or Grade ≥ 3 febrile neutropenia
- Grade 4 thrombocytopenia or Grade 3 thrombocytopenia accompanied by bleeding that requires any transfusion
- Grade 4 anemia or Grade 3 anemia requiring transfusion
- Grade 3 rash or Grade 3 endocrinopathies

- AST or ALT ≥ 3.0 and $\leq 5.0 \times \text{ULN}$ or TBL > 1.5 and $\leq 3 \times \text{ULN}$ (in subject with Gilbert's syndrome: AST or ALT ≥ 3.0 and $\leq 5.0 \times \text{ULN}$ or direct bilirubin $> \text{ULN}$) in subjects without liver metastases
- AST or ALT ≥ 3.0 and $\leq 8.0 \times \text{ULN}$ or TBL > 1.5 and $\leq 3 \times \text{ULN}$ (in subjects with Gilbert's syndrome: AST or ALT ≥ 5.0 and $\leq 8.0 \times \text{ULN}$ or direct bilirubin $> \text{ULN}$) in subjects with liver metastases
- Any Grade 2 or higher irAE (including but not limited to those listed below):
 - colitis or diarrhea
 - hypophysitis
 - adrenal insufficiency
 - nephritis
 - ocular inflammatory toxicity
 - pancreatitis
 - new-onset neurological symptoms or signs (other than Grade 2 or higher encephalopathy, meningitis or Grade 2 or higher motor or sensory neuropathy, which require permanent discontinuation of ASP1948 treatment)
 - IRR

Additionally, ASP1948 treatment may be interrupted for any AE, laboratory abnormality or intercurrent illness that in the judgment of the investigator warrants delaying dosing of ASP1948.

6.7.3 Criteria for Resuming Study Treatment

Dosing may be delayed for up to 12 weeks from the end of the prior treatment cycle for recovery of toxicity requiring IP treatment interruption. IP treatment may be resumed if the AEs have recovered to Grade 0 or 1 and steroid treatment tapered to physiological replacement doses (≤ 10 mg per day prednisone or equivalent) and do not meet the criteria for permanent discontinuation of study treatment. Interruption for COVID-19-related illness is limited to 12 weeks. Study treatment may be resumed in the absence of COVID-19-related symptoms per investigator judgement.

7 STUDY PROCEDURES AND ASSESSMENTS

7.1 Efficacy Assessments

7.1.1 Radiographic Assessment

Disease response and progression will be evaluated in this study using the RECIST 1.1 [Eisenhauer et al, 2009] and iRECIST criteria [Seymour et al, 2017] as assessed by the investigator.

Tumor assessments will be performed at Screening and at every 8 weeks (\pm 1 week) for Dose level A and Dose level B or every 9 weeks (\pm 1 week) for Dose level C from Cycle 1 Day 1 until confirmed disease progression by iRECIST (“immune” confirmed progressive disease [iCPD]). The assessment will include tumor measurements for target lesions, nontarget lesions and assessment for any new lesions. An overall assessment will be characterized for that time point.

CT or MRI scans are preferred for this study and to ensure comparability, the same technique (CT/MRI) used at Screening should be utilized throughout the study. The same method should be employed and assessed by the same individual on each occasion, when possible. Imaging should include chest, abdomen and pelvis as well as any other anatomical region appropriate for the subject’s disease.

Imaging should be performed every 8 weeks or 9 weeks from Cycle 1 Day 1 regardless of treatment interruption or delays. Scans performed prior to informed consent as standard of care are acceptable as screening scans if performed within 28 days prior to Cycle 1 Day 1.

Confirmatory scans for complete response (CR) or partial response (PR) should be performed at least 4 weeks after the date of the scan in which CR or PR was first observed.

Confirmatory scans for PD must be performed at least 4 weeks after the date of the scan in which PD was first observed, but no longer than 8 weeks.

Disease progression sites (including target, nontarget, new target, and new nontarget lesions) will be recorded in the eCRF.

7.1.2 Evaluation of Response at Each Time Point

The result of target lesion response, nontarget lesion response, new target lesion response, new nontarget lesion response and overall response assessment at each time point will be recorded in the eCRF according to the iRECIST.

7.1.3 Best overall response

Best overall response (BOR) on the study regimen should be assessed at the end of treatment for each subject according to RECIST 1.1 and iRECIST.

7.1.4 Tumor Response

Tumor size is defined as the sum of the diameters of all target lesions per RECIST 1.1. The percent change from baseline in tumor size will be calculated for subjects with target lesions at baseline. The best percent change in tumor size is the maximum percent reduction from

baseline, or if the subject has no reduction in size, the minimum percent increase from baseline.

7.2 Safety Assessments

Study procedures and their timing are summarized in the Schedule of Assessments ([Table 1](#), [Table 2](#), [Table 3](#) and [Table 4](#)). Protocol waivers or exemptions are not allowed.

Procedures conducted as part of a subject's routine clinical management (i.e., standard of care) obtained before signing the ICF may be utilized for Screening or baseline purposes, provided the procedures met the protocol-specified criteria and were performed within the time frame, as defined in the Schedule of Assessments.

7.2.1 Dose Limiting Toxicity (DLT)

Refer to [Section [4.1.4](#) Dose Limiting Toxicity Criteria].

7.2.2 Adverse Events

See [Section [7.3](#) Adverse Events and Other Safety Aspects] for information regarding AE collection and data handling.

7.2.2.1 Adverse Events of Possible Hepatic Origin

See [Appendix [12.5](#) Liver Safety Monitoring and Assessment] for detailed information on liver abnormalities, monitoring and assessment, if the AE for a subject enrolled in a study and receiving IP is accompanied by increases in liver function test (LFT) values (e.g., AST, ALT, bilirubin, etc.) or is suspected to be due to hepatic dysfunction.

Subjects with AEs of hepatic origin accompanied by LFT abnormalities should be carefully monitored.

7.2.3 Laboratory Assessments

Routine laboratory samples for complete blood count (CBC) with differential, serum chemistry, Hepatitis B and C testing, coagulation, urinalysis, urine or serum pregnancy, thyroid stimulating hormone (TSH) and free thyroxine (T4), testosterone and prostate specific antigen (PSA) (mCRPC only) will be collected and analyzed at the local laboratory. Laboratory assessments will be conducted and recorded at visits as outlined in the Schedule of Assessments. The local laboratory must be accredited to perform the protocol-required tests and a certificate of accreditation and laboratory normal ranges must be provided to the sponsor. See [Appendix [12.7](#) Laboratory Assessments] for the list of clinical laboratory tests to be performed and refer to the Schedule of Assessments ([Table 1](#), [Table 2](#), [Table 3](#) and [Table 4](#)) for timing and frequency.

Clinical significance of out-of-range laboratory findings is to be determined and documented by the investigator or subinvestigator who is a qualified physician.

7.2.4 Vital Signs, Height and Weight

Vital signs will include systolic and diastolic blood pressure (mmHg), radial pulse (beats/min) and temperature and will be obtained and recorded at the times specified in the

Schedules of Assessments (Table 1 and Table 2). All vital signs will be measured with the subject in the sitting or supine position.

Height and weight will be measured using standard institution practice and equipment and recorded at the times specified in the Schedules of Assessments (Table 1 and Table 2). If clinically significant vital sign changes from baseline (pretreatment) are noted, the changes will be documented as AEs on the AE page of the eCRF. Clinical significance will be defined as a variation in vital signs, which has medical relevance as deemed by the investigator that could result in an alteration in medical care.

7.2.5 Physical Examination

Physical examinations will be conducted and recorded at visits as outlined in the Schedule of Assessments (Table 1 and Table 2).

Standard, full physical examinations will be performed to assess general appearance, skin, eyes, ears, nose, throat neck, cardiovascular, chest and lungs, abdomen, musculoskeletal, neurologic status, mental status and lymphatic systems. Genitourinary and rectal system examinations are to be performed only if clinically indicated.

As a result of auscultation, a chest X-ray examination, sialylated carbohydrate antigen (Krebs von den Lungen-6) and transcutaneous arterial oxygen saturation may be performed if clinically indicated.

New or worsening clinically significant findings on physical examination will be recorded as AEs if they meet the criteria in [Appendix 12.4.1 Definition of Adverse Events].

7.2.6 Eastern Cooperative Oncology Group Performance Status

ECOG Performance Status will be conducted and recorded at visits as outlined in the Schedule of Assessments (Table 1 and Table 2).

The ECOG scale [Oken, 1982] will be used to assess performance status [see Appendix 12.12 Eastern Cooperative Oncology Group Performance Status Scale].

7.2.7 Electrocardiogram

ECGs will be conducted at visits as outlined in the Schedule of Assessments (Table 1, Table 2, Table 3 and Table 4). All recorded ECGs will be transmitted electronically for central reading.

ECGs should be obtained after the subject has rested quietly and is awake in a fully supine position (or semirecumbent, if supine is not tolerated) for 10 minutes before the first ECG from a triplicate or single ECG. For ECGs performed in triplicate, there should be at least 2 minutes between each ECG.

7.2.8 Order of Assessments

The following order should be followed when more than 1 assessment is required at a time point with blood sampling for pharmacokinetics/metabolic profiling being collected nearest to the scheduled time point:

1. ECG
2. Vital signs (blood pressure and heart rate)
3. Any type of blood draw as the last assessment

Note: This order of events can be changed if required in order to accommodate pharmacokinetic time points and is not mandatory

7.3 Adverse Events and Other Safety Aspects

The definitions of an AE or SAE can be found in [Appendix 12.4 Adverse Events: Definitions and Procedures for Recording, Evaluating, Follow-up or Reporting].

The investigator and medically qualified designee(s) are responsible for detecting, documenting and recording events that met the definition of an AE or SAE.

7.3.1 Time Period for Collecting Adverse Event and Serious Adverse Event Information

In order to identify any events that may be associated with study procedures and could lead to a change in the conduct of the study, Astellas collects AEs even if the subject has not received IP. AE collection begins after the signing of the ICF and will be collected until 30 days after the final IP administration or initiation of a new anticancer treatment, whichever comes first, or until the subject is determined to be a screen failure. SAEs (regardless of causality) will be collected from the time of informed consent through 90 days following the last dose of IP or until initiation of a new anticancer treatment, whichever comes first, or until the subject is determined to be a screen failure.

7.3.2 Method of Detecting Adverse Events and Serious Adverse Events

The methods of recording, evaluating and assessing seriousness, causality and severity of AEs and SAEs are described in [Appendix 12.4 Adverse Events: Definitions and Procedures for Recording, Evaluating, Follow-up and Reporting]. Care will be taken not to introduce bias when detecting AEs and/or SAEs. Open-ended and nonleading verbal questioning of the subject is the preferred method to inquire about AE occurrences.

An AE with a change in severity is recorded as a new AE.

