9.5.2 Adverse Events

AEs will be coded using MedDRA.

A TEAE is defined as an AE observed after starting administration of the IP and 30 days after the last dose of IP.

The number and percentage of subjects with TEAEs, SAEs, AEs leading to withdrawal of treatment, and AEs related to IP will be summarized by SOC, preferred term and dose level. The number and percentage of AEs by severity will also be summarized. All AEs will be listed.

An IP-related TEAE is defined as any TEAE with a causal relationship of YES by the investigator.

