9.11 Additional Conventions

9.11.1 Handling of Missing Data, Outliers, Visit Windows and Other Information

The final handling of missing data, outliers and visit windows will be decided before database lock, in reference to the opinions and advice of the DESC and the statistical advisor, as needed. The criteria for handling of analysis time points will be determined by taking acceptable visit windows specified in Table 1 and Table 2 into consideration. Subjects or data excluded from analyses will be listed but excluded from the tabulation of summary

statistics, etc. As a general principle, no imputation of missing data will be performed. Exceptions are the start and stop dates of AEs and concomitant medication. The imputed dates will be used to allocate the concomitant medication and AEs to a treatment group, in addition to determining whether an AE is/is not treatment-emergent. Listings of AEs and concomitant medications will present the actual partial dates; imputed dates will not be shown. See the SAP for details of the definition for windows to be used for analyses by visit.

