12.4.1 Definition of Adverse Events

An AE is any untoward medical occurrence in a subject administered an IP, and which does not necessarily have to have a causal relationship with this treatment. An AE can therefore be any unfavorable and unintended sign (including an abnormal laboratory finding), symptom, or disease (new or exacerbated) temporally associated with the use of IP whether or not considered related to the IP.

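### Every change of grade opens a new AE and severity is tabulated per AE, so an episode that rises and resolves is spread over several grade rows and the share of severe events is diluted

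*Protocol*

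**What the plan says.** Section 7.3.2 sets the recording rule: "An AE with a change in severity is recorded as a new AE". It does not limit the change to worsening, and nothing elsewhere in the protocol links the records of one episode.

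Section 9.5.2 sets the tables. For the main AE categories the unit is the subject: "The number and percentage of subjects with TEAEs, SAEs, AEs leading to withdrawal of treatment, and AEs related to IP will be summarized by SOC", then by preferred term and dose level. For severity the next sentence changes the unit: "The number and percentage of AEs by severity will also be summarized". No rule for worst grade per subject is given.

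Section 9.5.2 also defines treatment emergence: "A TEAE is defined as an AE observed after starting administration of the IP and 30 days after the last dose of IP". There is no condition that the event be new or worse than before dosing. Section 9.11.1 treats emergence as a matter of dates. Imputed start and stop dates serve to allocate events to a treatment group, "in addition to determining whether an AE is/is not treatment-emergent".

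Pre-dose AEs will be in the database, because under Section 7.3.1 "AE collection begins after the signing of the ICF and will be collected until 30 days after the final IP administration". Section 10.2.2 treats diseases unresolved at consent as complications. Appendix 12.4.1 describes an AE as an unfavourable sign, "symptom, or disease (new or exacerbated) temporally associated with the use of IP".

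**The concern.** AEs are part of the primary safety endpoint in Section 3, and the severity table is where a reader looks for how many of them were serious in grade. If the unit is the record and each step down in grade makes a record, severe events bring their own low-grade company into the denominator. An event that peaks at Grade 3 can leave more Grade 1 and 2 records behind it than an event that never left Grade 1. The dilution therefore falls on the events of most interest.

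Step-down courses are to be expected here. Section 6.7.3 lets dosing resume after recovery to Grade 0 or 1, and Section 7.3.3 has AEs followed to resolution or until they no longer matter clinically.

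The second issue is that a decrease in grade after first dose gives a record with a post-dose start date. By date alone it is treatment-emergent, although it documents an improvement.

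**Working it through.** The protocol states no figure on this point, so there is none to reproduce. The check applies the stated rules to assumed grade paths and compares the result with one count per episode at worst grade. All paths below are assumptions.

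**Severity table.** Share of severe events under the stated rules = records at Grade 3 or higher / all records. Comparison = episodes with worst grade 3 or higher / all episodes.

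| Assumed data | As written | Worst grade per episode |
|---|---|---|
| One episode 1-2-3-2-1 | 1/5 = 20% | 1/1 = 100% |
| One such episode + nine flat Grade 1 | 1/(5+9) = 1/14 = 7.1% | 1/10 = 10% |
| Five such episodes + five flat Grade 1 | 5/(25+5) = 5/30 = 16.7% | 5/10 = 50% |
| Five episodes 1-2-3, new record on worsening only, + five flat Grade 1 | 5/(15+5) = 5/20 = 25% | 5/10 = 50% |

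The last row shows that limiting new records to worsening would not be enough; the unit of the table has to change too. The second row shows that the effect is small when severe episodes are rare.

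The direction also depends on the path. An episode recorded only as 3-4-3, with nine flat Grade 1 episodes, gives 3/(3+9) = 3/12 = 25% against 1/10 = 10%. Understatement is the result for episodes that pass through lower grades on the way up or down.

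**TEAE definition.** Take an AE that starts at Grade 2 five days before first dose and falls to Grade 1 on Day 3.

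- Under Section 7.3.2 there are two records: Grade 2 (pre-dose) and Grade 1 (start Day 3).
- Under Section 9.5.2 the second record is observed after dosing began, so it is one TEAE.
- Under a rule of onset or worsening after first dose there is none.

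The window for such an event is the interval from consent to first dose, with Screening lasting up to 28 days (Section 4.1.1).

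One subject misclassified in this way shifts an incidence by 1/n: 1/3 = 33.3 points, 1/6 = 16.7 points and 1/9 = 11.1 points at the dose-level sizes the protocol names. For a preferred-term row the shift occurs if the subject has no other TEAE under that term. For overall TEAE incidence it occurs only if the subject has no other TEAE at all. Section 2.1.1.2.2 reports TEAEs in 8 of 9 subjects already treated in this study, and Section 2.1.1.2.1 in 84 of 91 on monotherapy in the first-in-human study. For most subjects the overall shift is therefore zero.

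**Other tables.** The tables by SOC and preferred term count subjects, so repeat records do not inflate them; they can inherit only the TEAE misclassification. The tolerability rule in Section 4.1.3 counts subjects with DLTs and is untouched.

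**The case against.** The strongest reply is that the wording on severity is merely loose. Sections 2.1.1.2.1 and 2.1.1.2.2 report Grade 3 or higher events by patient, for example 2 of 9 (22.2%) in this study, so the sponsor evidently thinks in subjects. Section 9 leaves table specifications to the SAP, where worst-grade collapsing would normally sit. All AEs will be listed, so in about 18 subjects each grade history can be read by hand. The grade paths above are constructed.

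Part of this stands. The size is not known, the listings limit the harm, and no dose decision depends on the table. But the interim summaries are not the planned table. The protocol is not silent on the unit: it names AEs directly after naming subjects, and it gives a TEAE definition. The SAP would have to override stated rules, not fill a gap.

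Three stronger readings are tempting and are not supported.

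- A reader might infer that improving baseline conditions in general become TEAEs. They do not. Conditions unresolved at consent are complications under Section 10.2.2, and Appendix 12.4.1 requires something new or exacerbated. Only AEs that start between consent and first dose are exposed.
- A reader might infer from the word observed that any pre-dose AE merely continuing after dosing counts. Section 9.11.1 makes emergence a test of dates, and nothing says that continuing events are included. A true worsening gets its own dated record and is already captured.
- A reader might infer that TEAE incidence is broadly inflated or that DLT assessment is distorted. The subject-level tables and the DLT rule show otherwise.

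**Conclusion.** The point holds for the severity table. As written, the recording rule and the event-based unit together split one episode over several grade rows and understate the share of severe events whenever an episode passes through lower grades. In the illustrations the share falls from 10% to 7.1% in a mild case and from 50% to 16.7% in a heavy one. These figures rest on assumed grade paths and on sites applying the recording rule literally, decreases included.

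The TEAE effect is real but narrow: it is confined to AEs with onset between consent and first dose that improve after dosing. It alters overall TEAE incidence only for a subject with no other TEAE.

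This is a minor to moderate reporting correction to a table within the primary safety endpoint. It has no consequence for DLT counts or the tolerability decision.

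**What to change.** In Section 9.5.2:

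1. Replace the event-based severity summary with counts and percentages of subjects by worst grade, per SOC and preferred term.
2. Define a TEAE as an AE that starts, or worsens from its pre-dose grade, after first dose, keeping the existing 30-day limit after the last dose.
3. State that a record opened only because the grade decreased is not a new TEAE.

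The recording rule in Section 7.3.2 can stay, since it preserves the grade history and gives each worsening its own date. The cost is a change of wording and a small programming rule that links the records of one episode. No new data are needed.

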7.3.3 Follow-up of Adverse Events

All AEs occurring during or after the subject has discontinued the study are to be followed up until resolved or judged to be no longer clinically significant, or until they become chronic to the extent that they can be fully characterized by the investigator.

If after the protocol-defined AE collection period (see [Section 7.3.1 Time Period for Collecting Adverse Event and Serious Adverse Event Information]), an AE progresses to an SAE, or the investigator learns of any (S)AE (serious adverse event or adverse event) including death, where he/she considers there is reasonable possibility it is related to the IP or study participation, the investigator must promptly notify the sponsor.

7.3.4 Reporting of Serious Adverse Events

Prompt notification by the investigator to the sponsor of an SAE is essential, so that legal obligations and ethical responsibilities towards the safety of subjects and the safety of a study intervention under clinical investigation are met.

In the case of an SAE, the investigator must contact the sponsor by fax or email immediately (within 24 hours of awareness).

Procedures for reporting SAEs to the sponsor are described in [Appendix 12.4.5 Reporting Procedures for Serious Adverse Events].

7.3.5 Disease-related Events and/or Disease-related Outcomes Not Qualifying as Adverse Events or Serious Adverse Events

Under this protocol, the following event(s) will not be considered as an (S)AE:

- Disease progression: events including defined study endpoints that are clearly consistent with the expected pattern of progression of the underlying disease are not to be recorded as AEs. These data will be captured as efficacy assessment data as outlined in [Section 7.1 Efficacy Assessments]. If there is any uncertainty as to whether an event is due to anticipated disease progression and/or if there is evidence suggesting a causal relationship between IP and the event, it should be reported as an (S)AE. All deaths up to 90 days after the final administration of IP must be reported as an SAE, even if attributed to disease progression.
- Preplanned and elective hospital/clinical procedures/interventions or procedures for diagnostic, therapeutic or surgical procedures for a preexisting condition that did not worsen during the course of the clinical study. These procedures are collected per the eCRFs Completion Guidelines.

